4.2. Development and Mechanism of Action of Fazirsiran

Since Z-AAT protein accumulation is the underlying cause of hepatocyte injury in AATD, preventing Z-AAT synthesis is a rational step to prevent hepatic Z-AAT polymerization,

aggregate formation, and accumulation, and thus a logical approach for treating AATD-associated liver disease. This is supported by the lack of liver disease in AATD patients with null/null genotypes. These rare patients completely lack AAT synthesis. They present clinically with pulmonary disease, but since they have no hepatocyte production or accumulation of mutant AAT protein, they are devoid of liver disease.

One mechanism of preventing Z-AAT accumulation is through RNA interference (RNAi)mediated gene silencing of Z-AAT protein production. RNA interference (RNAi)-based therapeutics have the potential to silence the expression of any disease gene. RNAi is a naturally occurring process by which small interfering RNA oligonucleotides (siRNAs) trigger a sequence-specific down-modulation of gene expression. By delivering siRNAs targeting AAT sequences to the liver, it is possible to knock down expression of AAT messenger RNAs (mRNAs) in hepatocytes. This reduces the synthesis of Z-AAT proteins that are responsible for hepatic disease in AATD. Reductions in levels of Z-AAT protein production should allow for degradation of Z-AAT proteins already present, prevent further hepatocyte injury, reduce inflammation and fibrosis, and allow for hepatic healing. Knocking down Z-AAT protein production with resulting reduction of both mutant protein aggregates and fibrosis in the PiZZ transgenic mouse has been well demonstrated (Teckman et al., 2013). Based on findings in mouse models of AATD-associated liver disease and effective treatment of other hepatic diseases such as viral hepatitis, it is also expected that with effective reduction in necroinflammation, fibrosis and early cirrhosis should reverse, as well, with effective, chronic treatment.

Arrowhead Pharmaceuticals, Inc. has developed a drug candidate, fazirsiran (TAK-999, also referred to as ARO-AAT) to treat AATD-associated liver disease through an RNAi-mediated mechanism. Fazirsiran is a novel hepatocyte targeted RNAi trigger molecule which is conjugated to N-acetyl-galactosamine to facilitate hepatocyte endocytosis. Fazirsiran is highly effective at knocking down the AAT mRNA gene transcript and reducing the production of hepatic Z-AAT protein.

4.3. Fazirsiran Preclinical Pharmacology and Studies

Preclinical pharmacology of fazirsiran was evaluated in the PiZ transgenic mouse model of AATD liver disease and in cynomolgus monkeys. In the mouse model, treatment with fazirsiran resulted in dramatically reduced serum Z-AAT protein levels, which correlated with reduced liver Z-AAT mRNA levels. Multi-dose studies showed that mice treated with fazirsiran have less Z-AAT burden in their liver compared to saline-treated mice. Liver Z-AAT burden is determined by separating a liver homogenate into a soluble and insoluble fraction; the insoluble fraction represents aggregates of polymerized protein. As expected, these mice also showed reductions in hepatocyte necrosis, liver inflammation, and down-regulation of fibrosis-related genes. Importantly, hepatocyte necrosis and liver inflammation are also seen on histologic evaluation of human PiZZ patient livers. Fazirsiran treatment in cynomolgus monkeys resulted in a maximum reduction in circulating AAT of approximately 93% with 80% or greater knockdown sustained for more than 8 weeks after receiving two once every 4 weeks (Q4W) 3 mg/kg doses of fazirsiran. Further information on the preclinical pharmacology studies is provided in the Investigator's Brochure.

4.4. Fazirsiran Preclinical Pharmacokinetic and Product Metabolism Studies

Pharmacokinetic (PK) parameters for fazirsiran have been evaluated in both rats and monkeys. Results of these studies can be found in the Investigator's Brochure.

4.5. Fazirsiran Preclinical Toxicology Studies

Fazirsiran has been clinically well tolerated in rats and in non-human primate (NHP) toxicology studies. Details regarding Good Laboratory Practice (GLP) and non-GLP toxicology results are provided in the Investigator's Brochure.

4.6. Fazirsiran Clinical Pharmacology, Pharmacokinetic and Clinical Safety

Fazirsiran has been evaluated in the AROAAT1001 study which investigated the safety and pharmacodynamic (PD) effects of single and multiple doses of fazirsiran in a healthy volunteer population. Results of the AROAAT1001 study are available in the Investigator's Brochure. Fazirsiran is also being evaluated in an ongoing, open-label pilot Phase 2 study in patients with AATD liver disease (AROAAT2002 study). Results of an Interim Analysis of the AROAAT2002 study are available in the Investigator's Brochure.

4.7. Rationale for the Study

Intracellular mutant (Z-AAT) misfolded protein accumulation is the underlying cause of hepatocyte injury in AATD (Torres-Duran et al., 2018). Preventing hepatic accumulation of misfolded protein by silencing Z-AAT synthesis is a logical intervention for treating AATD associated liver disease. This is supported by the development of liver tumors and upregulation of fibrosis associated genes in the PiZ transgenic mouse model and by the lack of liver disease in AATD patients with null/null genotypes versus the presence of liver disease in PiZZ genotype patients (Feldman et al., 1975). This is supported by improvement in liver histology, reduced liver Z-AAT protein (soluble and insoluble aggregates) and reduced fibrosis associated gene expression seen in PiZ mice treated with siRNA targeting the SERPINA1 gene product (Wooddell et al., 2016). Treatment of patients with fazirsiran is expected to reduce hepatic production of Z-AAT, leading to reductions in intrahepatic misfolded soluble and insoluble aggregated Z-AAT protein and reduction in serum AAT levels. Data obtained from nonclinical pharmacology studies in the PiZ mouse model have demonstrated that multiple doses of fazirsiran administered every other week for 4 doses can prevent the accumulation of, and even reduce the burden of already present Z-AAT protein in the livers of PiZ mice (Wooddell et al., 2020). Based on this animal data, it is expected that multi-dose treatment with fazirsiran in AATD patients will prevent further accumulation of intrahepatic mutant protein while allowing endogenous clearance mechanisms to remove Z-AAT protein already accumulated. This removal of the offending agent should reduce/eliminate inflammation, which should prevent further liver injury while allowing fibrosis due to earlier injury to remodel. The ability of the liver to heal with removal of an inciting insult has been demonstrated with treatment of other causes of liver

injury including hepatitis B virus (HBV), hepatitis C virus (HCV), and nonalcoholic fatty liver disease (NAFLD)/ nonalcoholic steatohepatitis (NASH) (Ellis et al., 2012).

The AROAAT2001 design and conduct is supported by existing nonclinical pharmacology and toxicology data as well as data from a Phase 1 clinical study AROAAT1001 in healthy volunteers which evaluated safety, PK, and PD effect of single and multiple escalating doses of fazirsiran. AATD patients with AATD associated liver disease will require multiple doses of fazirsiran to sustain hepatic silencing of AAT production. Accordingly, this study uses multiple doses of fazirsiran with each dose after the second dose administered approximately every 3 months.

Three different dose levels are being tested. The dosing regimen utilized in this study is supported by the PD effect and safety profile of three once every 28 days (Q28) doses of fazirsiran, which was evaluated in the AROAAT1001 study. Single dose PD effect from the AROAAT1001 study indicates that AAT serum protein levels generally reach nadir, but not always full suppression to below lower limit of quantitation around Week 6 to 8 and start to rebound by approximately Week 12 after a single dose. This observed time until rebound supports quarterly dosing. This study also demonstrated that a second dose at Day 29 (4 weeks after initial dose) resulted in complete suppression of circulating AAT levels that was sustained. (See Investigator's Brochure for details.) Based on these results, it was determined that 2 doses administered 28 days apart would quickly lead to maximal and sustained reduction in hepatic AAT production but thereafter dosing could be quarterly. Hence, this was viewed as the best approach to achieve the fullest level of hepatic reduction of the insulting agent while minimizing overall patient exposure by moving to quarterly dosing.

Based on non-clinical studies in the PiZ mouse model and experience with liver recovery from other necro-inflammatory diseases such as viral hepatitis, it is highly likely that dose administration beyond 3 doses will be required to reduce insoluble aggregated liver Z-AAT sufficiently to reduce globule inflammation and hopefully allow repair of hepatic architecture. Based on other precedents as discussed above, improvement of fibrosis or other adverse liver histologic findings due to AATD liver disease may require long-term therapy to show improvement.

The current study uses liver biopsy to obtain tissue samples to directly measure drug effect on hepatic Z-AAT protein and histopathology. Noninvasive measures (including serum biomarkers, FibroScan®, and magnetic resonance imaging [MRI]) of PD effect are also included. However, liver biopsy remains the gold standard for histological evaluation in clinical studies and is required to obtain tissue specimens for analysis of intrahepatic Z-AAT levels.

4.8. Risk Assessment for Patients

Based on the safety review of nonclinical and clinical trials, the following are considered as identified risks or potential risks:

Identified risks:

• Injection Site AE Risk: Adverse events (AEs) at the injection site (e.g., erythema, pain, etc.) have been reported with administration of fazirsiran in clinical studies AROAAT1001, AROAAT2001, and AROAAT2002 and are therefore considered an identified risk. All were deemed to be non-serious and resolved without sequelae. The majority of the injection site reactions (ISRs) were mild in severity. Other siRNA antisense oligonucleotides (ASOs) in clinical trials have been associated with usually mild ISRs. This study includes directions for assessing injection site AE intensity based on pre-defined criteria (see Section 10.5.2). Additionally, steps will be taken to minimize ISRs such as rotating injection sites and allowing the fazirsiran solution to come to room temperature prior to injecting.

Potential risks (monitored in this study using diagnostic evaluations, assessments, and study modification rules):

- Liver Biopsy Risk: Performance of liver biopsies is commonly part of the standard of care in patients with liver disease related to AATD as well as other adult liver diseases. While it is a common procedure, like any procedure it is associated with some risk. See Appendix 5 for more information about risks associated with study assessments such as liver biopsy.
- Pulmonary Risk: AATD may manifest as pulmonary disease in adult patients. AATD pulmonary disease is often treated with AAT augmentation therapy in countries where this therapy has been approved and is available. Fazirsiran is intended to reduce hepatic production of AAT and will, by extension, reduce serum levels of AAT protein. In AATD patients, this protein is poorly functional in its capacity to inhibit neutrophil elastase relative to wild type protein. Pulmonary disease in AATD requires decades to develop, especially in the absence of smoking, and it is extremely unlikely that short-term reduction in serum AAT will worsen pulmonary disease, particularly in non-smokers. The Sponsor anticipates an approximate 90% reduction of serum AAT to represent near maximum reduction possible with a hepatocyte targeted RNAi mechanism based on previous experience. Extra-hepatic production, including locally in the lung, is not expected to be reduced by fazirsiran.

Based on the lack of a consistent pattern of adverse changes in pulmonary function metrics seen in the AROAAT1001 study using siRNA to transiently reduce serum AAT levels, and the fact that the native Z-AAT has reduced inhibitory effect against neutrophil elastase, the reduction of serum Z-AAT should not significantly impact any protective effect. Pulmonary disease in PiZZ patients with very low serum AATD takes decades to develop. PiZZ patients already have very low serum AAT levels and a further reduction in already low AAT may not influence pulmonary function. Additionally, many of these patients are on AAT augmentation therapy or may be given augmentation therapy and will continue it during the trial. Steps will be taken in this study to mitigate this theoretical risk.

1. Patients who smoke or with a significant smoking history will be excluded from this study and their non-smoking status will be confirmed by measuring urinary cotinine at Screening and with repeat confirmatory checks during the study. Patients with a positive

urine cotinine during the study (with positive result confirmed on repeat) will be counseled on the importance of not smoking during the study.

- 2. Patients with severe and unavoidable exposure to inhaled environmental exposure will be excluded.
- 3. Above standard of care pulmonary monitoring is implemented during the study with vital capacity (VC), forced vital capacity (FVC), forced expiratory volume in one second (FEV₁), ratio of the forced expiratory volume in the first one second to the forced vital capacity of the lungs (FEV₁/FVC), and the ratio of the forced expiratory volume in 1 second to vital capacity (FEV₁/VC), measured pre-dose and at every dosing visit. Diffusing capacity for carbon monoxide (DLCO) is measured every dosing visit through Week 16 and then every other dosing visit.
- 4. Patients without sufficient pulmonary reserve at baseline (e.g., post-bronchodilation FEV₁ <65 % of predicted) are excluded. Patients with recent lower respiratory infections (such as pneumonia) are also excluded.
- 5. Standard of care emphysema treatment (e.g., corticosteroids, bronchodilators) is permitted.
- 6. Any patient developing pulmonary symptoms or worsening pulmonary function tests (PFTs) while on study will be referred to a pulmonologist for consideration of AAT augmentation therapy, which will be provided by the Sponsor if not otherwise available locally and if indicated in the opinion of the treating pulmonologist (See Pulmonary Study Modification Rules in Appendix 3).
- 7. Arrowhead will review all VC, FVC, FEV₁, and DLCO test results on a weekly basis during Safety Review Team meetings. Pulmonary function test results will be exported directly from the clinical trial database and any resulting decreases >10% from baseline will be identified. A query will be sent to the Investigator to confirm a pulmonary consultation has been requested and further dosing will be suspended for this patient until the consultation has occurred. Arrowhead follow up with sites will occur in order to obtain the pulmonologist evaluation.
- 8. The AROAAT2001 study will have a Data Safety Monitoring Board (DSMB). The DSMB Members will review all pulmonary function data and, in particular, review the patient data holistically where a FEV₁ >10% decline from baseline occurs. The Data Safety members will review those patients in an unblinded manner when deemed necessary to promptly identify if an imbalance in treatment groups occurs. It is the DSMB's responsibility to make recommendations to Arrowhead regarding the study conduct (including patient discontinuation from the study per protocol) in a manner that preserves the study blind as appropriate.
- **Hepatic Risk:** Fazirsiran targets the hepatic synthesis of AAT. Arrowhead has not seen a pattern of adverse transaminase changes in the AROAAT1001 healthy volunteer single

ascending doses/multiple ascending doses study. Others developing siRNA for AATD have seen evidence of mild to moderate elevations in transaminases using hepatocyte-targeted siRNA conjugates similar to those used by the Sponsor. It has been described that these alanine aminotransferase (ALT) changes were due to off-target effects of the siRNA seed region on microRNAs in the hepatocyte (Vaishnaw et al., 2017; Schlegel et al., 2017). The siRNA sequence of the fazirsiran sense and antisense molecules have been screened for potential mRNA and microRNA homology and sequences with homology were excluded from consideration. Thus, no such off-target effects are anticipated. In chronic GLP toxicity studies in rats and monkeys, adverse liver findings were not identified, with the no-observedadverse-effect levels (NOAELs) of 120 mg/kg in rats and 180 mg/kg in monkeys, which in both cases were the highest doses tested. Given the very large safety margins based on the chronic GLP toxicity study NOAELs, liver toxicity in humans is not expected. However, to further mitigate this risk of adverse liver findings, the proposed study protocol has built in stopping rules for ALT elevation applicable to patients who may have elevated ALT at baseline. Blood samples will be drawn frequently to evaluate liver injury and liver function. The DSMB will include hepatologists experienced in adjudication of drug induced liver events. Additionally, the planned doses used in this study of 25, 100, and 200 mg are approximately 1/336th, 1/84th, and 1/42nd, respectively (assuming weight-based conversion and a 70-kg subject) of the rat NOAEL of 120 mg/kg and 1/504th, 1/126th, and 1/63rd, respectively, of the 180 mg/kg monkey NOAEL from chronic GLP toxicity studies. Additionally, the doses used in this study are lower than the 300 mg dose level which was administered for 3 Q28 doses in the AROAAT1001 study and was well tolerated.

Additional information about identified and potential risks is provided in the Investigator's Brochure.

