Treatment Stopping and Study Modification Rules:

A decision to stop the trial early or discontinue drug in an individual patient or group of patients **may** be indicated based on any of the following:

- 1. In the case of 2 or more similar SAEs both considered at least possibly related to fazirsiran, the DSMB will meet within 3 days of the DSMB being notified of the second event and within the timeframe of required regulatory agency notification. The DSMB will review available aggregated data to determine if the study remains safe to proceed, should be discontinued, or should continue but with amendments.
- 2. Evaluation and fazirsiran study modification/discontinuation rules for elevated ALTs or worsening hepatic function (i.e., cirrhosis) and drug induced liver injury (DILI) are provided in Appendix 2.
- 3. Evaluation and fazirsiran study modification/discontinuation rules for declines in pulmonary function are provided in Appendix 3.

Table 1: Schedule of Assessments for Patients Without Fibrosis at Screening

			Day 1 24 hrs After		Week	Week	24 hrs After	Week	Week		Follo	w-Up Peri	od	Early	
Assessment	Scree	en	(Dosing Day)	Day 1 Dose	2	4	Day 29 Dose	6	16	Week 28	Week 40	Week 52	Week 64: Study Completion	Term- ination ⁵	
	Required Day				Day 15	Day 29 (Dosing Day)		Day 43	Day 113	Day 197	Day 281	Day 365	Day 449		
Windows (in days)	-60 to -1	-30 to -1		+1	± 5	±5	+1	± 5	± 14	± 14	± 14	± 14	± 14		
Informed Consent	X														
Eligibility Criteria	X														
Demographics/Medical History	X														
PiZZ Genotype	Х														
Height, Weight, & BMI	х														
Weight only			X			X			X	X	X	X	Х	X	
Urine Cotinine	X								X					X	
Urine Drug Screen	X														
Hepatitis/HIV	X														
PFT (Spirometry and DLCO) ¹		X	Pre-dose X			Pre-dose X			X	X 1	X	X ¹	X	x	
FibroScan [®]	X												X	X	
MRI (PDFF, Fe, MRE) ²	X												X	X	
Liver Biopsy ⁶	X														
Vital Signs (BP, temperature, HR, RR)	x		Pre-dose & 1 hr post-dose X	X	х	Pre-dose & 1 hr post-dose X	X	X	X	X	X	X	x	x	
Physical Exam ³	X		Pre-dose X	X	X	Pre-dose X	X	X	X	X	X	X	X	X	
ECG 7	X		Pre-dose X			Pre-dose X			X	X 7	X	X 7	Х	X	
Urine Pregnancy Test ⁸	Х		Pre-dose X			Pre-dose X			Х	Х	Х	Х	X	Х	

Table 1: Schedule of Assessments for Patients Without Fibrosis at Screening (continued)

Assessment Screen			Day 1 (Dosing Day)	24 hrs After	Week 2	Week 4	24 hrs After	Week 6	Week 16		Follo	w-Up Peri	od	Early Term-				

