9.3.3. Pulmonary Function Testing

Spirometry and DLCO will be conducted at timepoints outlined in the SOA for all patients. When conducted on dosing days, spirometry and DLCO are to be conducted pre-dose. Spirometry will be conducted in a pulmonology laboratory or at the clinical site in accordance with American Thoracic Society and European Respiratory Society (ATS-ERS) guidelines (Graham et al., 2019) and each patient will undergo pulmonary function testing at the same location throughout the study. DLCO assessment will be conducted in accordance with ATS-ERS guidelines (Graham et al., 2017). All spirometry and DLCO values collected and recorded will include both pre- and post-bronchodilation measurements (unless contraindicated or unavailable).

Spirometry: Spirometry will include VC, FVC, FEV₁, FEV₁/VC, and FEV₁/FVC, all of which will be recorded in the eCRF.

Bronchodilator: At least 3 pre-bronchodilator maneuvers will be performed, followed by administration of a bronchodilator (generally 90 μg albuterol per puff or 100 μg salbutamol per puff), unless contraindicated or unavailable. A site may elect to not perform bronchodilation on certain study subjects if that is in accordance with the site's standard of practice. Following the administration of the bronchodilator, at least 3 post-bronchodilator maneuvers will be performed.

The best pre- and post-bronchodilation measurements should be documented in an eCRF as follows:

- The best FEV₁ is the largest volume FEV₁ from an acceptable maneuver
- The best FVC is the largest volume FVC from an acceptable maneuver
- The best FEV₁/FVC is the best FEV₁ divided by the best FVC, even if these values come from different maneuvers

The number of puffs of bronchodilator administered should be documented, as this information will be captured on the pulmonary function testing eCRF. If administration of bronchodilator during spirometry is not aligned with the institution's practice, the CRA will be notified to ensure Sponsor notification and appropriate study file documentation.

DLCO: The DLCO assessment may be performed either pre- or post-bronchodilation. At least 2 maneuvers should be attempted. The DLCO value recorded in the eCRF should be the average of 2 or more acceptable, repeatable maneuvers.

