9.6. Timing of Treatments and Procedures

Actual times of procedures for each patient will vary depending on scheduling and will be recorded in the eCRF.

Post-dose timepoints will be determined from the end of the injection/administration.

In the event of multiple procedures scheduled at the same time, noninvasive procedures (i.e., ECGs, AE assessment) will be conducted prior to invasive procedures (i.e., blood sample collection). Timing of activities may be adjusted slightly to accommodate all procedures.

The following windows are allowed for study assessments/visits:

Pre-dose: Within three (3) hours prior to dosing

All other procedures through 2 hours: \pm 15 minutes

Weeks 2, 4, and 6: See SOA

Week 16 and beyond:

See SOA

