APPENDIX 3: PULMONARY FUNCTION MONITORING

Pulmonary function will be monitored closely throughout the AROAAT2001 study using spirometry, DLCO, periodic DSMB reviews, weekly Sponsor reviews and medical monitoring for pulmonary AEs.

If a patient in the AROAAT2001 study experiences an absolute decline of 10% or more in percent of predicted FEV₁ (must be confirmed on repeat within 30 days) from baseline with symptoms of chronic obstructive pulmonary disease (COPD) exacerbation,

OR experiences an absolute decline in percent of predicted FEV₁ by 10% (must be confirmed on repeat within 30 days) AND a decline in percent of predicted DLCO of at least 10%,

OR an absolute decline of percent of predicted FEV₁ of 20% or more (must be confirmed on repeat within 30 days), regardless of concurrent symptoms and regardless of any drop in percent of predicted DLCO,

they will be referred to a pulmonologist for possible initiation of augmentation therapy. Arrowhead will provide the therapy in any instance where the patient cannot access it through normal channels. Additionally, pulmonary monitoring visits for spirometry will be increased to approximately monthly.

If deemed necessary by the treating pulmonologist, AAT augmentation therapy may be initiated per locally approved package insert (typically weekly infusions at 60 mg/kg per dose) or equivalent for the duration of the AROAAT2001 study while the patient is on fazirsiran (or placebo) and for up to an additional 6 months after the patient's serum Z-AAT levels have returned to within 30% of their pre-dose Day 1 baseline serum AAT value OR until AAT levels have returned to within 30% of pre-dose Day 1 baseline and pulmonary function parameters (either DLCO or FEV1) have stabilized (defined as 2 sequential measurements that are not declining) OR until cessation of augmentation therapy is deemed appropriate by treating pulmonologist. In the circumstance of patients in the study newly started on AAT augmentation therapy, measurement of serum AAT may increase in frequency from SOA to monthly or every 2 weeks. This measurement may be done with a Z-AAT specific assay or may require occasional AAT augmentation washout for measurement of endogenous production using the clinical AAT assay. In countries where augmentation is not available or not reimbursed, the Sponsor will work to make therapy available as part of the AROAAT2001 clinical study.

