Each patient newly started on augmentation therapy during the study due to declines in FEV₁ and/or DLCO as described above will be reviewed by the DSMB to assess if the patient should continue to receive treatment with fazirsiran or placebo. Additionally, the DSMB will evaluate for imbalances in adverse changes in FEV₁, DLCO and pulmonary AEs in active versus placebo groups at each planned DSMB meeting.

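### Appendix 3 contains no pulmonary dose hold, and the hold in Section 4.8 normally comes too late for the dose due on the day a fall is first measured

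*Protocol*

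**What the plan says.** The synopsis (Treatment Stopping and Study Modification Rules, item 3) and Section 6.3 both state: "Evaluation and fazirsiran study modification/discontinuation rules for declines in pulmonary function are provided in Appendix 3".

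Appendix 3 sets three triggers based on an absolute fall in percent-predicted FEV₁, each to be confirmed by a repeat within 30 days. For patients who meet one, "they will be referred to a pulmonologist for possible initiation of augmentation therapy", and spirometry becomes roughly monthly. Its one decision about continuing study treatment is a DSMB case review, whose scope is "Each patient newly started on augmentation therapy during the study due to declines in" FEV₁ or DLCO. No sentence in Appendix 3 holds, interrupts or suspends a dose.

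The hold is in Section 4.8, pulmonary item 7. The sponsor looks at VC, FVC, FEV₁ and DLCO "test results on a weekly basis during Safety Review Team meetings". The results are "exported directly from the clinical trial database and any resulting decreases >10% from baseline will be identified". The site is then queried about the pulmonary consultation, and "further dosing will be suspended for this patient until the consultation has occurred".

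On timing, Section 9.3.3 says: "When conducted on dosing days, spirometry and DLCO are to be conducted pre-dose". Section 9.6 defines the interval: "Pre-dose: Within three (3) hours prior to dosing".

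**The concern.** A site that follows the cross-reference to Appendix 3 finds when to refer a patient, but not whether to inject. The hold itself depends on a central process that runs weekly, while the injection is due within 3 hours of the test. So a site can follow every written rule and still dose a patient whose FEV₁ was found that morning to be more than 10% below baseline. That is the same fall for which the sponsor has decided to suspend dosing.

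Section 4.8 lists lung decline as a potential risk, and Section 4.9 expects serum AAT to start to rebound only about 12 weeks after a dose. A dose given on the day of the finding therefore acts for most of the interval to the next one.

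**Working it through.** **1. Dosing schedule (synopsis; Table 2).** With fibrosis, doses fall on Day 1, Week 4 and Week 16, then every 12 weeks to Week 196: 3 + (196 − 16)/12 = 3 + 15 = 18, the plan's own maximum. At Week 100: 3 + (100 − 16)/12 = 3 + 7 = 10, which agrees with the plan's 10th dose.

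**2. Doses preceded by a same-day test that could show a fall.** The Day 1 test is the baseline, so:
- With fibrosis: 18 − 1 = 17, or 10 − 1 = 9 if dosing stops at the 10th dose.
- Without fibrosis: 2 − 1 = 1. Week 4 is both the first scheduled post-baseline test and the last dose (Table 1), so on scheduled tests item 7 could never have stopped a dose in these patients.

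**3. Speed of the hold.** Test to injection takes at most 3 hours. Test to weekly review takes up to about 7 days, assuming results are entered promptly. The review cannot be relied on to act before that day's injection.

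**4. The next dose the hold can reach (windows from Table 2).**
- Nominal: Day 113 − Day 29 = 84 days.
- Week 4 (±5 days) to Week 16 (±14 days): minimum 84 − 5 − 14 = 65 days.
- Week 16 onward (±14 days at both visits): minimum 84 − 14 − 14 = 56 days.

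All of these exceed 7 days, so the weekly review normally does protect the next dose. The gap is the same-day dose only.

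**5. What can still change.** Sections 6.1, 8.7 and 11.11 say in the past tense that all enrolled patients had completed Week 16. Patients without fibrosis have no doses left. Each patient with fibrosis has at most 10 − 3 = 7 further doses (Weeks 28 to 100), or 18 − 3 = 15 at the maximum, less any already given. After the post-dose biopsy these are all active 200 mg, including in patients first randomised to placebo.

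**6. Scale of item 7.** Item 7 gives no scale for its 10%. Read as relative to baseline:
- At the 65% predicted entry floor, 0.10 × 65 = 6.5 points; at 100%, 10 points.
- A fall from 65 to 57 is 8 points, or 8/65 = 12.3%. It exceeds 10% relative but not 10 absolute points.
- A 10-point fall from 65 is 10/65 = 15.4% relative, so an absolute gate would be looser than item 7 for the patients with least reserve.

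**7. Comparison with other rules in the same protocol.**

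| Signal | Written dosing instruction |
|---|---|
| Pregnancy test (Table 2 footnote 9; Section 9.3.6) | Result needed before the dose; no dose if positive |
| Liver tests (Appendix 2) | Study drug interrupted at stated thresholds |
| Lung function (Appendix 3) | None |
| Lung function (Section 4.8, item 7) | Suspension after the weekly central review |

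**The case against.** The best defence is that the plan manages a lung decline by treating it. Appendix 3 requires confirmed falls, and symptoms or a DLCO decline as well for a 10-point fall. It then offers augmentation, supplied by the sponsor if necessary, while study treatment continues. Spirometry is noisy, so an automatic hold on one reading would delay doses needlessly. The sponsor or investigator may discontinue any patient at any time (Sections 6.3 and 7.4), item 6 of Section 4.8 already requires referral, and unscheduled tests follow a COPD exacerbation or an Appendix 3 trigger. Section 4.8 regards short-term worsening as extremely unlikely.

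Much of this stands. Expected harm is small, and discretion and extra tests lessen the gap. But a power to stop is not a rule to stop, referral is not a hold, and item 7 shows that the sponsor did want dosing suspended for these falls. Noise can be handled with the one repeat per timepoint that Table 2 footnote 1 allows.

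A reader might infer more than the documents support:

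- **That the cross-reference leads nowhere.** Appendix 3 does give evaluation triggers, closer monitoring and a DSMB continuation review. What it lacks is a dose hold.
- **That the item 7 and Appendix 3 thresholds contradict each other.** They can be read as two tiers, one for consultation and one for augmentation. Appendix 3 says so expressly when it means absolute percent-predicted points, so the natural reading of item 7 is relative.
- **That a visit count measures the problem.** If 24 patients with fibrosis reach dose 10 and 12 without fibrosis reach Week 4, then 24 × 9 + 12 × 1 = 228 visits pair spirometry with a later-than-Day-1 dose. Of these, 24 × 2 + 12 = 60 are past, leaving at most 168. Both totals include saline doses given before the biopsy, and neither counts falls in lung function.

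**Conclusion.** The point holds as a cheap improvement. Appendix 3 has no dose hold, and the only mandatory patient-level hold does not, as written, act on the dose due within 3 hours of the test that first shows the fall. It normally acts on the next dose, nominally 84 days later.

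This rests on reading item 7 literally: the fall is identified through the weekly export, and only later doses are suspended. It also assumes that no earlier unscheduled test has already revealed the fall. If the sponsor intends an immediate hold at the site, the protocol does not say so where sites are told to look.

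The benefit is confined to doses still due in patients with fibrosis. The documents give neither a rate of decline nor a time to consultation, so the number of patients affected or doses delayed cannot be estimated.

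**What to change.** In Appendix 3:

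1. Cross-reference the item 7 hold, and state that its 10% is relative to the value before the first dose of the study. Naming that baseline matters because the SAP Addendum (Section 4) resets baseline at the first open-label dose for its own summaries.
2. Add that at each dosing visit the site compares pre-dose FEV₁ (post-bronchodilator where done) with that baseline before injecting. If it is down by more than 10%, use the one repeat already allowed. If the fall persists, defer the dose until the pulmonary consultation. With a baseline of 65, the 65-to-57 case would be deferred, since 57 is below 65 − 6.5 = 58.5.
3. Keep the weekly sponsor review as the backstop for VC, FVC and DLCO. DLCO may be only six-monthly from Week 28, so it cannot serve as a check at every visit. Leave the augmentation criteria unchanged.

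The cost is a short text amendment and a comparison using a test already done; no new test or visit is needed. A few doses would be delayed, some because of spirometry noise or a transient fall that the repeat does not remove, and some beyond the ±14-day window. Where a pulmonology laboratory performs the spirometry, as Section 9.3.3 permits, it must pass the result to the site before the injection.
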